4.6. Safety Analyses

Safety analyses will be conducted using the Safety Analysis Set. Baseline values for all safety analyses will be defined as the last observation prior to dosing.

4.6.1. Study Drug Exposure

Duration of drug exposure will be defined as (the last dose of study drug – the first dose of study drug + 21)/30.44 months. Duration of drug exposure and duration of infusion will be summarized using descriptive statistics. Summaries of the numbers and percentages of subjects with a dose reduction, any missing dose, and the numbers of missed doses per subject, will be provided. Duration of interruption will be summarized using descriptive statistics. Summary statistics will also be provided for the total volume infused.

All data related to study drug administration will be presented in a data listing.

4.6.2. Adverse Events

All AEs will be coded using the MedDRA coding system and displayed in tables and data listings using system organ class (SOC) and preferred term.

Analyses of AEs will be performed for those events that are considered treatment-emergent, where treatment-emergent is defined per protocol as any AE with onset during or after the administration of study medication through 28 days following the last dose of study drug. In addition, any event that was present at baseline but worsened in intensity or was subsequently considered drug-related by the Investigator through the end of the study will be considered treatment-emergent. Events with a fully or partially missing onset date will be assumed to be treatment emergent unless it can be unequivocally determined (from the partial onset date and/or a partial or complete stop date) that the event occurred prior to the first administration of study medication.

AEs are summarized by the numbers and percentages of subjects reporting a given AE. Therefore, in any tabulation, a subject contributes only once to the count for a given AE (overall, by SOC, by preferred term).

Tabulations by SOC and preferred term will be produced for all AEs, for all AEs related to study medication, for all severe AEs, for all AEs leading to study discontinuation, and for all serious AEs. Separate summary tables will be provided characterizing signs and symptoms of IRRs and AEs related to pre-medications. The incidence and frequency of IRRs over time will also be provided. AEs and serious AEs will be also summarized for Cardiac Subgroup. AEs will be tabulated by preferred term in decreasing order in frequency.

Separate tables will present AE incidence by maximum relationship to study drug and by maximum severity. Subjects who report multiple occurrences of the same AE (preferred term) will be classified according to the most related or most severe occurrence, respectively.

No formal hypothesis-testing analysis of AE incidence will be performed.

All AEs occurring on-study will be listed in subject data listings. A separate listing will be provided for IRRs. Listings will be provided for any AEs caused by pre-medications or any study procedure.

By-subject listings will also be provided for the following: subject deaths, SAEs, and AEs leading to discontinuation.

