8.4 Adverse Event Reporting

The Investigator is responsible for reporting all AEs that are observed or reported after the first dose of study drug regardless of their relationship to study drug through the 21 or 56-day Follow-up visit (depending on whether or not the patient plans to enroll into the open-label global extension study).

Any medical condition that is present when a patient is screened and does not deteriorate should not be reported as an AE. However, if it does deteriorate at any time during the study, it should be reported as an AE.

All AEs must be fully recorded in the site's source records and in the patients' CRF, whether or not they are considered to be drug-related. Each AE should be described in

detail: onset time and date, description of event, severity, relationship to investigational product, action taken, and outcome (including time and date of resolution, if applicable).

Adverse events should be followed for the reporting periods defined earlier or until recovery to the normal state has been achieved, whichever occurs first. In the event of a patient not returning to the clinical unit, the outcome of this event will be recorded as lost at follow-up.

For patients who withdraw from the study early, ongoing AEs will be followed until resolution or 28 days from last dose, whichever occurs first.

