8.5 Adverse Event Reporting Period

As stated in [Section 8.4](#), AEs will be assessed for 21 or 56 days following the last dose of study drug (depending on whether or not the patient plans to roll over to the open-label global extension study) or until recovery to the normal state has been achieved, whichever occurs first; all AEs that occur after the start of study drug administration on Day 0 (Baseline) must be reported in detail on the appropriate CRF page and followed to satisfactory resolution, or a period of 21 or 56 days after the last dose of study drug administration (depending on whether or not the patient plans to roll over to the open-label global extension study), whichever is shorter.

Serious AEs will be followed for 21 or 56 days following the last dose of study drug (depending on whether or not the patient plans to roll over to the open-label global extension study), or until satisfactory resolution, or until the SAE is considered by the Investigator to be chronic or the patient is stable, whichever occurs first.

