- w Use of all concomitant medications during Screening/Baseline, predose, and postdose will be recorded on the patient's CRF up to the 21-day or 56-day Follow-up visit (depending on whether or not the patient plans to roll over to the open-label global extension study).
- x Adverse events are to be documented beginning with the initiation of the first infusion through the 21-day or 56-day Follow-up visit (depending on whether or not the patient plans to roll over to the open-label global extension study).

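### SAP 4.6.2 attributes a 28-day treatment-emergent window to the protocol, which sets none; late new AEs in patients who do not roll over would probably be listed but not tabulated (minor)

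*SAP*

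**What the plan says.** SAP 4.6.2 opens its analysis rule with "Analyses of AEs will be performed for those events that are considered treatment-emergent" and states that treatment-emergent is "defined per protocol as any AE with onset during or after the administration of study medication through 28 days following the last dose". It adds events already present at baseline that "worsened in intensity or was subsequently considered drug-related by the Investigator through the end of the study". Events with a missing or partial onset date count as treatment-emergent unless they clearly began before the first dose. The section then announces tabulations for all AEs and all serious AEs, without saying whether these are limited to treatment-emergent events. For listings it says "All AEs occurring on-study will be listed in subject data listings", with separate by-subject listings of deaths and SAEs.

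The protocol names TEAEs in the synopsis and in 9.2 and 9.2.3 but attaches no onset window to the term. Section 8.4 makes the investigator report all AEs "regardless of their relationship to study drug through the 21 or 56-day Follow-up visit", depending on whether the patient plans to enter the extension. Section 8.5 says "AEs will be assessed for 21 or 56 days following the last dose of study drug". Table 1-2 note x, which the SAP reproduces in 1.2.4, reads "Adverse events are to be documented beginning with the initiation of the first infusion through the 21-day or 56-day Follow-up visit". The protocol's one AE rule set at 28 days after dosing is in 8.4 and concerns patients who withdraw early: "ongoing AEs will be followed until resolution or 28 days from last dose, whichever occurs first".

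**The concern.** Two things look wrong. First, the SAP credits the protocol with a rule that the supplied protocol does not contain. The only 28-day AE rule there concerns how long to follow events already under way in early withdrawals; it does not decide which new events count. Second, the 28-day cut-off is shorter than the reporting period for patients who do not roll over, so sites would be asked to report events that the analysis then leaves out of the tables.

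Safety is the primary objective and the incidence tables are its main summary. Protocol 1.3 reports that, after a single dose in healthy volunteers, TTR began to recover around Day 21-28 and returned to baseline by Day 70. That does not show that late AEs will occur, but it does mean that a cut-off at 28 days should carry a stated reason. The documents give none.

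**Working it through.** **Is there a protocol window?** Setting the texts side by side:

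| Source | Rule | Applies to |
|---|---|---|
| SAP 4.6.2 | onset through 28 days after last dose, credited to the protocol | all patients |
| Protocol 8.4, 8.5, Table 1-2 note x; SAP 1.2.4 note x | AEs through the 21-day visit | rollover patients |
| Same | AEs through the 56-day visit | non-rollover patients |
| Protocol 8.4 | ongoing AEs followed at most 28 days from last dose | early withdrawals |
| Protocol 9.2, 9.2.3 | TEAE tabulated, no window | all patients |

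The 28 days is a definition, not a computed figure, so there is nothing to reproduce. What can be checked is the length of time it leaves out.

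**Inputs.** From the every-3-week schedule (Table 1-2): last dose Day 735, 21-day visit Day 756, 56-day visit Day 791, visit window ±5 days, dosing window ±3 days. Check: 735 + 21 = 756 and 735 + 56 = 791. Enrollment is up to 28 (SAP 3.1). The number not rolling over is not given, so I show the full range.

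**Nominal loss per non-rollover patient.** The cut-off falls on Day 735 + 28 = 763. Days outside the window: 791 - 763 = 28, which is 28/56 = 50% of the reporting period after the last dose.

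**Allowing for visit windows:**
- Visits timed from the actual last dose, as protocol 6.2.5 suggests: the 56-day visit falls 51 to 61 days after it, leaving 51 - 28 = 23 to 61 - 28 = 33 days outside.
- Visits timed by study day, with the last dose on Day 732 to 738: the 56-day visit falls 786 - 738 = 48 to 796 - 732 = 64 days after it, leaving 20 to 36 days outside.
- Rollover patients: the 21-day visit falls 16 to 26 days after the last dose (nothing lost) or, by study day, 751 - 738 = 13 to 761 - 732 = 29 days after it (at most 1 day lost).

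**Share of all AE observation time.** Assume 28 patients enroll and complete, and k do not roll over. Share = 28k / [791k + 756(28 - k)].

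| k | Calculation | Share |
|---|---|---|
| 0 | 0 / 21,168 | 0% |
| 7 | 196 / 21,413 | 0.9% |
| 14 | 392 / 21,658 | 1.8% |
| 21 | 588 / 21,903 | 2.7% |
| 28 | 784 / 22,148 | 3.5% |

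These are shares of calendar time, not of events. The documents give no basis for estimating how many AEs begin in that period.

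**The case against.** The strongest reply is that SAP 4.6.2 does not plainly exclude late events. It says that AEs are shown in tables as well as listings, and it promises tabulations of all AEs and all serious AEs. This stands in part. The sentence restricting analyses to treatment-emergent events probably governs, but the section does not settle it. A reader might infer that late AEs and SAEs are definitely dropped from every table; the text supports that only as the likelier reading.

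A second reply is that the SAP may rest on another version of the protocol. It mentions magnetic resonance neurography and a suicidality questionnaire that the supplied protocol lacks, and it gives up to 19 patients in the PK/PD subgroup against up to 25. SAP Section 5, where a departure would be declared, shows no text after its lead-in, and it cannot be told whether anything was there. So the statement about the missing window is limited to the supplied protocol. Nothing shows that another version contains it.

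Third, a reader might infer that the clause on worsened or later-related events has no usable end date, or that it brings in new late AEs judged drug-related. Neither inference is well supported. Protocol 4.5 and SAP 3.8 tie completion to the 21- or 56-day visit, which gives the end of the study a natural meaning for each patient. The subject of the clause is events present at baseline.

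Fourth, a common 28-day cut-off has merit, because a pooled full-period percentage would mix 21-day and 56-day follow-up. This also stands. It argues for keeping 28 days as a stated choice, but not for crediting it to the protocol.

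**Conclusion.** The attribution is unsupported by the supplied protocol and should be corrected. On the likelier reading of SAP 4.6.2, new AEs with a known onset nominally 29 to 56 days after the last dose in non-rollover patients would be listed but not tabulated. The share of AE observation time affected lies between zero (all roll over) and about 3.5% (none does), assuming 28 completers on the every-3-week schedule. For early withdrawals, the documents are less clear about collecting new AEs after day 28, and the calculation leaves those patients out.

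A reader might go further and infer that the safety tables fall short of the reporting period for the whole study, or that a safety conclusion is distorted. The documents do not support this. For rollover patients the 28-day window is nominally longer than the reporting period, and the number of non-rollover patients may be zero. All on-study AEs are listed, deaths and SAEs have their own listings, undated events default to treatment-emergent, and no hypothesis is tested. The point is minor.

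**What to change.** In SAP 4.6.2:
1. Delete the attribution to the protocol.
2. State whether the tabulations of all AEs and all serious AEs cover treatment-emergent events only.
3. Either define treatment-emergent through the end of the protocol AE reporting period, or keep 28 days as the main view, give the reason, and add one tabulation of AEs and SAEs with onset after day 28 through the end of that period.
4. For the clause on worsened or later-related events, state that the end of the study means the patient's 21- or 56-day visit.

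The cost is a few sentences plus one flag or table, using data that protocol 8.4 already requires. The late-onset table may be nearly empty. Keeping it separate avoids most of the mixing of follow-up lengths.

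Separately, the protocol needs reconciling on AE recording at the 56-day visit. Section 6.2.5.1 includes AE documentation at the 21-day visit, whereas 6.2.5.2 lists only blood samples at the 56-day visit, although 8.4, 8.5 and Table 1-2 note x carry AE reporting to that point.

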4.5.2 Handling of Withdrawals

In the event a patient is withdrawn from the study, the contract research organization (CRO) Medical Monitor must be informed immediately. If there is a medical reason for withdrawal, the patient will remain under the supervision of the Investigator for protocol-specified safety follow-up procedures.

Patients who voluntarily withdraw are termed dropouts. Dropouts will not be replaced.

If a patient is withdrawn/withdraws every effort should be made to conduct the ET visit. Patients who fail to return for final evaluations will be contacted by the site in an attempt to have them comply with the protocol. The site will follow-up by telephone at least twice and send a registered letter to any patient who fails to return for the final evaluation.

When a patient withdraws from the study, the primary reason for discontinuation must be recorded in the appropriate section of the CRF and all efforts will be made to complete and report the observations as thoroughly as possible.

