5.7 Criteria for Dose Modification or Discontinuation of Study Drug

If a study drug related AE occurs in a patient that the Investigator judges as presenting a potential risk to the patient for further dosing, the Medical Monitors and Investigator will review all available safety data for that patient and for all other patients enrolled in the study. Based on this review it may be decided to discontinue further administration of ALN-TTR02, or, if the Investigator concurs, the patient may resume ALN-TTR02 as before or any of the following modifications may be instituted for that patient: reduce the dose of ALN-TTR02 to 0.15 mg/kg, modify the premedication regimen, and/or increase the number of weeks between dosing.

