9.2 Statistical Methodology

Statistical analyses will be primarily descriptive in nature. Adverse event summaries will include tabulations of all treatment-emergent AEs (TEAEs), treatment-related AEs, SAEs, discontinuations due to AEs, and AEs of various grading severity. By-patient listings will be provided for deaths, SAEs, and AEs leading to discontinuation of treatment.

Descriptive statistics will be provided for clinical laboratory data, vital signs data, and ECG interval data, presented as both actual values and changes from baseline relative to each on-study evaluation. Laboratory shift tables from baseline to worst values will be presented.

For categorical variables, summary tabulations of the number and percentage of patients within each category (with a category for missing data) will be presented. For continuous variables, the number of patients, mean, median, standard deviation, minimum, and maximum values will be presented.

All data will be provided in by-patient listings.

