9.2.3 Safety Analyses

A summary of study drug exposure, including the durations of the infusions and doses, and the proportions of patients with modifications in the durations of infusions will be produced.

Adverse events will be summarized by MedDRA system organ class and preferred term. Separate tabulations will be produced for all TEAEs, treatment-related AEs (those

considered by the Investigator as at least possibly drug related), SAEs, and discontinuations due to AEs. By-patient listings will be provided for deaths, SAEs, and AEs leading to discontinuation of treatment.

Descriptive statistics will be provided for clinical laboratory data and vital signs data, presented as both actual values and changes from baseline relative to each on-study evaluation and to the last evaluation on study.

Descriptive statistics will be provided for ECG interval data and presented as both actual values and changes from baseline relative to each on-study evaluation and to the last evaluation on study. Details of any abnormalities will be included in patient listings.

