4. STUDY ANALYSES

4.1. Subject Disposition

Subject disposition will be tabulated and include the number enrolled, the number dosed with patisiran, the number who completed the study, the number in each subject population for analysis, the number who withdrew prior to completing the study and reason(s) for withdrawal.

A by-subject data listing of study completion information including the reason for premature study withdrawal will be presented.

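### No SAP table counts patients who stopped patisiran because of an adverse event: SAP 4.6.2 tabulates only AEs leading to study discontinuation, and SAP 4.1 counts only study withdrawals

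*SAP*

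**What the plan says.** **Protocol.** Under 9.2, AE summaries are to "include tabulations of all treatment-emergent AEs (TEAEs), treatment-related AEs, SAEs, discontinuations due to AEs, and AEs of various grading severity". Section 9.2.3 repeats the item at the end of its list of separate tables: "considered by the Investigator as at least possibly drug related), SAEs, and discontinuations due to AEs". Neither sentence says what is discontinued. The listing sentence in 9.2 does: "By-patient listings will be provided for deaths, SAEs, and AEs leading to discontinuation of treatment". Section 9.2.3 has the same listing.

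**SAP.** Section 4.6.2 specifies tables by system organ class and preferred term for all AEs and related AEs, and then "for all severe AEs, for all AEs leading to study discontinuation, and for all serious AEs". Its by-subject listings cover "subject deaths, SAEs, and AEs leading to discontinuation", with neither drug nor study named. In disposition, SAP 4.1 gives the numbers enrolled, dosed and completed, the number in each analysis population, and "the number who withdrew prior to completing the study and reason(s) for withdrawal". The exposure summaries in SAP 4.6.1 cover duration, dose reductions, missed doses and interruptions. They do not include permanent stopping or its reason.

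**Stopping drug and leaving the study.** Protocol 5.7 deals with a drug-related AE that may make further dosing risky: "Based on this review it may be decided to discontinue further administration of ALN-TTR02". It does not say whether the patient then leaves the study. Withdrawal from the study is handled in Protocol 4.5.

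**The concern.** In a single-arm study of long-term dosing, one of the first tolerability results a reader looks for is the number of patients who could not stay on drug because of an AE. The only kind of discontinuation that the protocol's statistical section names is discontinuation of treatment. The only kind that the SAP's AE tables name is discontinuation of the study. If the two can differ for a patient, the report can show no AE discontinuation for someone whose treatment was ended by an AE, and no other specified table would correct that impression.

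**Working it through.** The documents give no figure on this point, so there is none to reproduce. The check compares the texts, and simple proportions show the scale.

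**1. Which event each output covers**

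| Output | Protocol 9.2 and 9.2.3 | SAP 4.1 and 4.6.2 |
|---|---|---|
| AE table | Discontinuation, kind not stated | Study discontinuation |
| By-patient listing | Discontinuation of treatment | Discontinuation, kind not stated |
| Disposition | Not specified | Study withdrawal and reasons |

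No cell in the SAP column is a count of patients who stopped drug because of an AE.

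**2. Can a patient stop drug for an AE and not be counted?** SAP 3.8 treats a patient as a completer after the Year 2 efficacy assessments and either the 21-day or the 56-day follow-up visit. It does not require dosing to have continued. Protocol 6.2.5 sets the follow-up visits from the last dose received.

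An example uses the 3-weekly schedule in Protocol Table 1-2, where the last planned doses fall on Days 693, 714 and 735 and the annual assessment on Day 749. Suppose a patient has a last dose on Day 693 and then stops for an AE.

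- Planned doses not given: Days 714 and 735, so two. Protocol 4.5.1 and 5.8 call for a decision on continuing after three consecutive missed doses.
- 21-day follow-up: 693 + 21 = Day 714.
- 56-day follow-up: 693 + 56 = Day 749, the same day as the annual assessment.

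This patient can meet SAP 3.8 in full and would be a completer with no AE leading to study discontinuation.

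A second route is a patient who stops drug for an AE and later leaves for a different primary reason, such as withdrawn consent. Protocol 4.5.2 and SAP 3.8 record the primary reason for discontinuation.

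**3. Scale.** The maximum N is 28 (Protocol 9.1, SAP 3.1). Let x be the number who stop drug for an AE but are not recorded as leaving the study for it. The documents do not give x, so it is an assumption, shown from 0 to 3. The proportion is x/28. The exact 95% limits are the 2.5% point of Beta(x, 28 − x + 1), taken as 0 when x = 0, and the 97.5% point of Beta(x + 1, 28 − x).

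| x assumed | Stopped drug for AE | Exact 95% CI | Same patients in the SAP table |
|---|---|---|---|
| 0 | 0% | 0 to 12.34% | 0 |
| 1 | 3.57% | 0.09 to 18.35% | 0 |
| 2 | 7.14% | 0.88 to 23.50% | 0 |
| 3 | 10.71% | 2.27 to 28.23% | 0 |

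**4. Direction.** A patient who leaves the study for an AE during the dosing period has also stopped drug, whereas one who stops drug need not leave. That makes the SAP count too low. The reverse can also occur. A patient who receives the last dose on Day 735 and leaves because of an AE before the Day 749 assessment is an AE study discontinuation without having stopped drug early.

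**The case against.** The strongest reply is that the two events will coincide for most patients. A serious or intolerable AE is a listed reason for study withdrawal in Protocol 4.5.1. For a medical withdrawal, Protocol 4.5.2 says "the patient will remain under the supervision of the Investigator for protocol-specified safety follow-up procedures", so safety follow-up goes on while the patient is classed as withdrawn. The protocol has no visit schedule for someone off drug but still on study. The AE also remains in the overall, severity, relationship and, where applicable, serious AE tables. With at most 28 patients, the dosing and AE listings would let a careful reader trace a stop.

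Most of this stands, and it rules out three stronger readings that a reader might infer.

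- *The protocol defines the tabulated event as treatment discontinuation and the SAP replaced it.* The protocol attaches treatment only to the listing, and its tabulated item is unspecified. Reading that item as treatment is an inference from the neighbouring sentence. The SAP narrowed an ambiguous term.
- *Anyone who stops drug for an AE and stays for follow-up is lost from the count.* A patient who has only safety follow-up, without the Year 2 assessments, is a non-completer under SAP 3.8. That patient is counted if the AE is the recorded reason.
- *The rule can only make tolerability look better.* Step 4 of the working gives a case in the other direction.

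The objection does not supply the missing count. Being able to reconstruct a main tolerability result from listings is not the same as specifying it. Nor do the documents close the two routes in step 2, although they do not describe either as a planned pathway.

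**Conclusion.** The point holds in a limited form. The SAP specifies no table of patients who stopped patisiran because of an AE, and its one discontinuation table counts a different event. The patients affected are those who stop drug for an AE and either complete the Year 2 assessments and a follow-up visit or leave later for another recorded reason. For them the AE is still reported, but not as a cause of stopping drug.

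Each such patient is 3.6 percentage points at N = 28. How many there will be is unknown, and there may be none. The effect will usually favour tolerability. This rests on reading Protocol 5.7 as a drug-level decision that does not by itself end participation. Its text allows that reading but does not state it. No planned calculation changes, and nothing here bears on when drug should be stopped. The gap is modest, but it touches the primary objective and should be closed.

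**What to change.** - **SAP 4.6.2:** tabulate and list AEs leading to permanent discontinuation of study drug, and separately AEs leading to study withdrawal. Name the event in the listing title as well.
- **SAP 4.1:** add the number of patients who discontinued treatment early, with the reason, apart from study withdrawal.
- **Derivation:** state how permanent discontinuation for an AE is identified, from the dosing record together with the AE and discontinuation data. This is needed because the action-taken list in Protocol 8.8 covers no action, an infusion interrupted and restarted, an infusion stopped and not restarted, and a delayed cycle. None of these clearly means permanent withdrawal of drug.

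The cost is one extra table, one disposition row and a short derivation rule. No additional visits are needed. Where the records do not make the reason for stopping clear, some case-by-case review may be required, for at most 28 patients.
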